7.5.2 Other Efficacy Analyses

7.5.2.1 Follow-up Therapy

Subsequent therapy will be summarized and listed using the treated population.

- Chemotherapy by drug name
- Immunotherapy by drug name (including anti-PD1 or anti-CTLA4 agents)
- Tyrosine kinase inhibitor by drug name
- Other investigational agent by drug name
- Surgery
- Radiotherapy
- Any combination of the above

In addition, a by subject listing will also be presented for tumor response and lesion evaluation using the treated population.

7.6 Safety

Safety data will be presented for all treated subjects by ECOG PS subgroups (PS 0-1 and PS2) and worst grade per NCI CTCAE (any grade, grade 3-4, and grade 5). Safety and tolerability will be measured by the incidence of all adverse events, serious adverse events, deaths, and laboratory abnormalities. Adverse event assessments and laboratory tests will be performed at baseline, and continuously throughout the study at the beginning of each subsequent cycle.

7.6.1.2 Select Adverse Events

Categories of “select AEs” have been created to group together the most common and impactful preferred terms (PTs) by organ category, providing a better estimate of the frequency of similar kinds of organ-related AEs instead of using PTs only. These select adverse events are further defined as follows:

- may differ from or be more severe than AEs caused by non-immunotherapies
- may require unique (non-standard) intervention such as immunosuppressants (or hormone replacement therapy)
- early recognition and management may mitigate severe toxicity

The preferred terms included in the ‘select AEs’ category are those that are expected to be most commonly used to describe pneumonitis, interstitial nephritis, diarrhea/colitis, hepatitis, rash, and endocrinopathies. Hypersensitivity/infusion reactions are also considered a select AE category to facilitate the pooling of the most relevant preferred terms for analyses of hypersensitivity/infusion reaction events and not because such events fit the criteria for select AEs.

Select AEs are based on the list provided by BMS every 6 months.

Unless otherwise specified, analysis will be performed by select AE category and ECOG PS group: Some analyses may also be repeated by subcategory of endocrine events.

- Overall summary of any select AEs overall and by worst CTC grade presented by Category or Subcategory/PT A presentation of by age category will also be provided. Overall summary of drug-related select AEs by worst CTC grade presented by Category or Subcategory / PT
- Overall summary of any serious select AEs by worst CTC grade presented by Category or Subcategory /PT
- Overall summary of drug-related serious select AEs by worst CTC grade presented by Category or Subcategory /PT. A presentation of by age category will also be provided.
- Overall summary of serious select Endocrine AEs by worst CTC grade presented by Category or Subcategory /PT
- Overall summary of drug-related serious select Endocrine AEs by worst CTC grade presented by Category or Subcategory /PT
- Overall summary of any select AEs leading to discontinuation overall and by worst CTC grade presented by Category or Subcategory /PT

- Overall summary of drug-related select AEs leading to discontinuation overall and by worst CTC grade presented by Category or Subcategory /PT

The analyses will be conducted using the 30-day safety window and repeated using the 100-day safety window.

By-subject select AE listing will be provided.

7.6.2 Secondary Analyses

7.6.2.1 Time-to onset of select AE

Time-to onset of the following specific events will be graphically displayed for each category/subcategory of select AEs using the Kaplan-Meier technique:

- Time-to onset of any grade select AE by ECOG PS subgroup
- Time-to onset of grade 3 to 5 select AE by ECOG PS subgroup
- Time-to onset of any grade drug-related select AE by ECOG PS subgroup
- Time-to onset of grade 3 to 5 drug-related select AE by ECOG PS subgroup

Rates (derived from the graph) by landmark timepoints will be tabulated for these specific events and for each subgroup.

Additional details regarding the time-to onset definition and censoring rules are described in time-to onset definition subsection of APPENDIX 1 of the Core SAP.

The analyses will be conducted using the 30-day safety window and repeated using the 100-day safety window.

Time-to onset of the following specific events will be presented in a table for each category/subcategory of select AEs by ECOG PS subgroup:

- Summary of time to onset of select adverse events overall and by worst CTC grade presented by Category or Subcategory / PT
- Summary of time to onset of drug-related select adverse events overall and by worst CTC grade presented by Category or Subcategory / PT

7.6.2.2 Time-to resolution of select AE

Time to resolution of the following specific events will be summarized separately for each category/subcategory.

- Time-to resolution of select AE by ECOG PS subgroup
- Time-to resolution of drug-related select AE by ECOG PS subgroup

Time-to resolution analyses are restricted to treated subjects who experienced the specific events.

The following summary statistics will be reported: percentage of subjects who experienced the specific events, percentage of subjects with resolution of the longest select AE, median time-to resolution along with 95% CI (derived from Kaplan-Meier estimation) and ranges.

See time-to resolution definition subsection of APPENDIX 1 of the Core SAP for additional details.

The analyses will be conducted using the 30-day safety window and repeated using the 100-day safety window.

[REDACTED]

- [REDACTED]

- [REDACTED]

- [REDACTED]

- [REDACTED]

- [REDACTED]

[REDACTED]

[REDACTED]

[REDACTED]

[REDACTED]

- [REDACTED]

- [REDACTED]

- [REDACTED]

[REDACTED]

[REDACTED]

[REDACTED]

- [REDACTED]

- [REDACTED]

- [REDACTED]

[REDACTED]

[REDACTED]

7.6.4 Decimal Places

Decimal places should follow GBS General Requirements Statistical Outputs.

7.7 Interim Analyses

Not applicable.

7.8 Other Analyses

Other analyses include the percentage of subjects who received immune-modulating medication or hormone replacement therapy.

Additional exploratory analyses will be performed ad hoc and as necessary to address queries from the regulatory authorities.

8 CONVENTIONS

Unless otherwise noted, the following conventions should be understood to apply. Further conventions may be detailed in the Data Presentation Plan.

The duration between two dates will be calculated as [later date] – [earlier date] + 1 day. Study Day 1 or first dose date is the date of first study medication. Study day associated with an assessment will be calculated as [assessment date] – [first dose date (or randomization date for non-treated subjects)]. If the assessment is on or after first dose/randomization then 1 is added to the calculation.

The following factors will convert days to months or years: 1 month = 30.4375 days, 1 year = 365.25 days.

Conventions for Partial/Missing Dates

Unless specified otherwise the following conventions will be used for imputing partial dates:

- If only the day of the month is missing, the 15th of the month will be used to replace the missing day.
- If both the day and the month are missing, “July 1” will be used to replace the missing information.
- If a date is completely missing, it will be considered as missing.

For date of death:

- If only the day of the month is missing, the 1st of the month will be used to replace the missing day*.
- If both the day and the month are missing, “Jan 1” will be used to replace the missing information*.

- If date is missing, death date will be imputed as the last known alive date.
 - * The imputed death date will be compared with the last known alive date (date of censoring for survival). If the death date is not equal to the date of censoring for survival then the maximum of the (imputed death date, date of censoring for survival) will be considered as the date of death.

For date of progression:

- If only the day of the month is missing, the 1st of the month will be used to replace the missing day*.
- If the day and month are missing or a date is completely missing, it will be considered as missing.
 - * In case, the date of death is present (complete date), the imputed progression date will be compared with the date of death. The minimum of the (imputed progression date, date of death) will be considered as the date of progression.

For date of last tumor assessment:

- If only the day of the month is missing, the 1st of the month will be used to replace the missing day*.
- If the day and month are missing or a date is completely missing, it will be considered as missing.
 - * In case, the date of death is present (complete date), the imputed date will be compared with the date of death. The minimum of the (imputed date, date of death) will be considered as the date of last tumor assessment.

For adverse events of special interest onset date:

- If only the day of the month is missing, the first of the month will be used to replace the missing day.
- If the day and month are missing or a date is completely missing, it will be considered as missing.

For adverse events of special interest resolution date:

- If only the day of the month is missing, the last of the month will be used to replace the missing day.
- If the day and month are missing or a date is completely missing, it will be considered as missing.

Otherwise, missing values will not in general be imputed.

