6.2.1 Nonserious Adverse Event Collection and Reporting

The collection of nonserious AE information should begin at initiation of study drug. All nonserious adverse events (not only those deemed to be treatment-related) should be collected continuously during the treatment period and for a minimum of 100 days following the last dose of study treatment.

Nonserious AEs should be followed to resolution or stabilization, or reported as SAEs if they become serious (see [Section 6.1.1](#)). Follow-up is also required for nonserious AEs that cause interruption or discontinuation of study drug and for those present at the end of study treatment as appropriate. All identified nonserious AEs must be recorded and described on the nonserious AE page of the CRF (paper or electronic).

Completion of supplemental CRFs may be requested for AEs and/or laboratory abnormalities that are reported/identified during the course of the study.

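### SAP section 8 imputes partial select-AE onset and resolution dates without plausibility bounds, so literal use gives onsets before first dose and resolutions after death

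*SAP*

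**What the plan says.** SAP section 8 (Conventions) has separate partial-date rules for adverse events of special interest. That is the former name of select adverse events; SAP section 2.4 records the change of term under Amendment 1.

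- Onset, day missing: "If only the day of the month is missing, the first of the month will be used to replace the missing day".
- Resolution, day missing: "If only the day of the month is missing, the last of the month will be used to replace the missing day".

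Neither rule carries a footnote or a comparison with another date. Three other date types in the section do:

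- Death: "The imputed death date will be compared with the last known alive date", and the later of the two is used.
- Progression: "The minimum of the (imputed progression date, date of death) will be considered as the date of progression", where the death date is complete.
- Last tumor assessment: "The minimum of the (imputed date, date of death) will be considered as the date of last tumor assessment", under the same condition.

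On collection, Protocol section 6.2.1 states: "The collection of nonserious AE information should begin at initiation of study drug". Serious events are collected from consent (Protocol section 6.1.1).

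SAP section 6.1 defers study periods to the Core Safety SAP. SAP sections 7.6.2.1 and 7.6.2.2 defer the time-to-onset and time-to-resolution definitions to Appendix 1 of the Core SAP. Section 8 allows for further conventions in the Data Presentation Plan. None of these three documents is available here.

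**The concern.** Select adverse events form the primary endpoint, and their times to onset and resolution are secondary endpoints. The partial-date rules therefore feed the main results.

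The onset rule moves the date back to the start of the month. If that is also the month of first dose, the imputed onset precedes treatment unless dosing began on the 1st. For a nonserious event this cannot be right, because collection had not yet begun. The event then has a false time to onset and may drop out of the treatment period.

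The resolution rule moves the date forward to month-end. If the subject died, or the data were cut, earlier in that month, the event is recorded as resolving after the last day on which this could have happened or been seen.

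Because the section bounds three comparable dates, the gap looks like an oversight rather than a choice.

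**Working it through.** The plan gives no figure for this point, so there is none to reproduce. The check applies the section 8 rules literally to every day of a 365-day year, giving each day equal weight (assumption).

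**1. Onset in the month of first dose, day missing.** The imputed onset is the 1st, so it precedes first dose whenever first dose is not on the 1st. Twelve days in the year are a 1st.

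- Share before first dose: (365 − 12)/365 = 353/365 = 96.7%.
- Shift (day of month of first dose − 1): mean 14.7 days, maximum 30.
- With onset set to the later of the 1st and first dose: 0 of 365.

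**2. Worked onset case.** First dose is 20 September and onset is recorded as September. The true time to onset, counted as later − earlier + 1, lies between 1 day (20 September) and 30 − 20 + 1 = 11 days. The imputed onset is 1 September. The section 8 study-day formula gives 1 − 20 = day −19. The section 8 duration formula gives 20 − 1 + 1 = 20 days. Neither is a possible value. With the bound, onset is day 1.

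**3. Resolution in the month of death, day missing.** Month-end falls after death unless death is on the last day of a month.

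- Share after death: 353/365 = 96.7%, by up to 30 days.
- With resolution set to the earlier of month-end and death: 0 of 365.

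**4. Worked resolution case.** Onset is 2 March, death 10 March, and resolution is recorded as March. As written: 31 − 2 + 1 = 30 days. The most that is possible: 10 − 2 + 1 = 9 days.

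**5. How often the onset rule would bite.** Assume that onset after first dose is exponential with mean μ. For first dose on day D > 1 of a month with L days, the chance of onset in the same month is 1 − exp(−(L − D + 1)/μ). For D = 1 the contribution is zero, because the imputed date is then first dose itself. Averaged over the year:

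| μ (days, assumed) | Share of day-missing onsets imputed before first dose |
|---|---|
| 60 | 21% |
| 90 | 15% |
| 120 | 11% |

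These shares apply only to events with a missing onset day. If a fraction m of select adverse events has a missing day, the affected share of all select adverse events is m × 0.11 to m × 0.21. The documents do not give m.

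**6. The other end of the window.** SAP section 7.6.1.2 uses 30-day and 100-day safety windows. Suppose the last dose is 10 March, so that the 30-day window ends on 9 April, and the true onset is 20 April, recorded as April. The imputed onset is 1 April, and the event is counted inside the window. The same rule can therefore add events as well as remove them.

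**The case against.** The strongest case against is that the consequences rest on documents that were not available. Study periods and the two time-to-event definitions sit in the Core SAP, section 8 yields where something else is noted, and the SAP history records a revision to meet Core SAP and Data Presentation Plan requirements. A bound may exist there. This limits what can be claimed, but section 8 gives explicit rules for these dates and points to no bound, so a programmer following it would produce impossible dates.

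A reader might also infer more than the documents support:

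- *That the onset rule can only lower the primary incidence.* It cannot be said to do so, because of step 6. SAP section 7.6.1.1 also states no date filter for the primary count, so loss of an event from it is not shown.
- *That time to onset becomes negative.* Only the study day does. The section 8 duration formula gives a positive but false value, and the time-to-onset formula itself is in the Core SAP.
- *That every such imputed date is wrong.* This holds for nonserious events. Serious events are collected from consent and screening may last 28 days, so a serious event dated to the month of first dose may truly have begun before treatment.
- *That one lost event is material, as in 4/800 (0.50%) becoming 3/800 (0.375%).* The plan uses counts of that size to illustrate precision for a single rare event. For Grade 3 and 4 select adverse events as a group, Protocol section 7 and SAP section 2.5 estimate a rate below 25%. Even at 200/800, one event moves the rate by 1/800 = 0.125 percentage points.

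Visits every two weeks and 24-hour reporting of serious events also suggest that few high-grade events will lack a day.

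**Conclusion.** The defect stands as a gap in a stated rule. When the day is missing and the onset month is that of first dose, the imputed onset of a nonserious select adverse event is impossible unless dosing began on the 1st. When the day is missing and the resolution month is that of death, the imputed resolution falls after death unless death was on the last day of the month. The error is at most 30 days per event in either case.

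Time to onset is distorted and time to resolution lengthened for the affected events; no effect on either median has been shown. Whether an affected event is classed as pre-treatment depends on the Core Safety SAP. The net direction of bias in incidence is undetermined. Its size is unknown, since no frequency of partial dates is given, and probably small.

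The change is worth making because the rule yields wrong dates for primary-endpoint events and is easily corrected. The conclusion assumes that section 8's old term means select adverse events. If it did not, the default mid-month rule would apply, and that has no bound either.

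**What to change.** Add two sentences to SAP section 8 under the select adverse event dates:

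1. If the recorded onset month and year are those of first dose and the imputed onset precedes first dose, set onset to the first dose date, unless other data (for example a serious adverse event report or a recorded resolution date) show that the event began earlier.
2. Set the imputed resolution date to the earliest of month-end, date of death and data cut-off.

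For a serious event whose timing stays ambiguous, the first sentence counts it from first dose, which is the conservative choice for a safety endpoint. Replace the old term with select adverse events in the same edit.

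If the Core SAP already contains these bounds, cross-refer to them at this place instead. The cost is two sentences and about one line of derivation code for each; no new data are needed.

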9 CONTENT OF REPORTS

The complete list of analyses contributing to the clinical study report is given in the Data Presentation Plan.

[REDACTED]

DOCUMENT HISTORY

Version Number	Date	[REDACTED]	Description
0.1	4 Sept 2015	[REDACTED]	Initial version
0.2	15 Oct 2015	[REDACTED]	Revision per BMS comments
0.3	20 Dec 2015	[REDACTED]	Revisions per BMS comments
1.0	15 Feb 2015	[REDACTED]	Revisions per client comments (version changed for finalization.)
1.1	17 June 2016	[REDACTED]	Revisions per Core SAP/DPP requirement
2.0	18 July 2016	[REDACTED]	Revisions per BMS comments
